8.8 Windowing Visits

Although there is a visit window of ± 7 days around the expected visit date, nominal visits will be used for the per-visit analyses. The data obtained outside the scheduled visits for certain procedures could be assigned to nominal visits, for instance, CSF GAGs or Neurodevelopment assessments. For subjects who withdraw from the study prematurely, if the early termination visit falls into the window of a scheduled visit as defined in the protocol, the early termination visit is also summarized for that scheduled visit, unless the scheduled visit already took place.

8.9 Data Listings

All data will be presented as SAS datasets in CDISC format. Unless specifically stated in above sections, no other by-patient data listings will be provided.

9. APPENDICES

9.1 Appendix I - List of Statistical Outputs

There are separate documents called “Table Shells” for the pivotal study and substudy, respectively, including Tables, Figures, and Listings.

9.2 Appendix II - Sample SAS code

Note that the dataset and variable names may be different in the real data.

9.2.1 Sample SAS code for the primary analysis

```
ods output estimates=est Tests3=FixF;
ods graphics on;
proc mixed data=adef data=adef covtest;
  class Trt VisitWk GCAclass Agegroup Genotype usubjid;
  model GCAchgBL = GCAclass Trt VisitWk Trt*Visitwk GCABL Agegroup Trt*GCAclass
  Trt*Agegroup GCAclass* Agegroup Genotype / ddfm=KR residual;
  repeated VisitWk / type=un subject=usubjid rcorr;
  estimate "Trt diff at Week 16" Trt 1 -1 Trt*VisitWk 1 0 0 0 -1 0 0 0 / cl;
  estimate "Trt diff at Week 28" Trt 1 -1 Trt*VisitWk 0 1 0 0 0 -1 0 0 / cl;
  estimate "Trt diff at Week 40" Trt 1 -1 Trt*VisitWk 0 0 1 0 0 0 -1 0 / cl;
  estimate "Trt diff at Week 52" Trt 1 -1 Trt*VisitWk 0 0 0 1 0 0 0 -1 / cl;
  lsmeans Trt*VisitWk / cl;
run;
```

9.2.2 Sample SAS code for the key secondary analysis

```
ods output estimates=est Tests3=FixF;
ods graphics on;
proc mixed data=adef data=adef covtest;
  class Trt VisitWk GCAclass Agegroup Genotype usubjid;
  model ABCchgBL = GCAclass Trt VisitWk Trt*Visitwk ABCBL Agegroup Trt*GCAclass
  Trt*Agegroup GCAclass* Agegroup Genotype / ddfm=KR residual;
  repeated VisitWk / type=un subject=usubjid rcorr;
  estimate "Trt diff at Week 16" Trt 1 -1 Trt*VisitWk 1 0 0 0 -1 0 0 0 / cl;
  estimate "Trt diff at Week 28" Trt 1 -1 Trt*VisitWk 0 1 0 0 0 -1 0 0 / cl;
  estimate "Trt diff at Week 40" Trt 1 -1 Trt*VisitWk 0 0 1 0 0 0 -1 0 / cl;
  estimate "Trt diff at Week 52" Trt 1 -1 Trt*VisitWk 0 0 0 1 0 0 0 -1 / cl;
  lsmeans Trt*VisitWk / cl;
run;
```

9.2.3 Sample SAS code for the EQ-3D analysis

```
proc npar1way data=adef ;
```

```
strata GCAclass Agegroup;  
class Trt;  
var VASchgBL;  
run;
```

9.2.4 Sample SAS code for the correlation analysis using repeated measures

```
ods output vcorr=vcorr;  
proc mixed;  
  class usubjid vtype replicate;  
  model response = vtype / ddfm=kr;  
  random vtype / type=un subject=usubjid v vcorr cl;  
  repeated vtype / type=un subject=replicate(usubjid) r rcorr;  
run;
```

usubjid corresponds to subject number; vtype refers to the two variables assessed, which are coded as 1 and 2; Response corresponds to the values of the two variables; and Replicate corresponds to the number of repeated measurements for each subject, which need not be the same.

9.2.5 Sample SAS code for rate of change in GCA score analysis

```
ods output ANOVA=ANOVA ParameterEstimates=Parms;  
proc reg data = subject_data ;  
  model GCA = VisitWk ;  
run ;Linear regression fit for individual subject data to calculate individual slope.
```

```
data weight;  
  set ANOVA(drop=Model DEPENDENT DF SS FVALUE PROBF);  
  weight=1/(1+MS);  
  if SOURCE='Error';  
run;
```

Two sample comparison:

```
proc glm;  
  class Trt;  
  model weighted_slope =trt;  
  lsmeans trt / pdiff CL;  
run;
```

where weighted slope=1/(1+MSE from linear regression fit)*slope.

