6. STATISTICAL ANALYSIS

6.1 General Methodology

All statistical analyses will be performed by the Biostatistics and Statistical Programming department at Shire unless otherwise specified, using SAS[®] software version 9.3 or higher (SAS Institute, Cary, N.C., USA).

Continuous variables will be summarized using descriptive statistics (N, mean, standard deviation, minimum, median, and maximum). Categorical variables will be summarized using the number and percentage of patients in each category. Data will be summarized with respect to patient disposition, demographic and baseline characteristics and concomitant medication use. The efficacy endpoints, safety assessments and other outcome results for each treatment group will be summarized descriptively unless otherwise indicated. In addition, statistical model estimates of least squares means, treatment differences, p-values and 95% confidence intervals for least squares mean treatment differences will also be provided where relevant for efficacy endpoints. The fit of linear models will be assessed using residual plots and/or other diagnostic plots as appropriate. All the statistical tests will be 2-sided and performed at the 0.05 level of significance unless stated otherwise. Baseline is defined as the value at Screening Visit for all parameters, unless specified otherwise. The planned analyses described below in this SAP pertain to the pivotal study data.

The separate substudy is an open-label, single arm study. Data from patients participating in this separate substudy will be analyzed separately. Since the number of patients enrolled in the substudy is expected to be low, their safety and efficacy data will not be summarized, but the corresponding data as described for the pivotal study will be listed. The listing format would be the same as that for the pivotal study where relevant.

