6.7.1 Primary Analysis

For the pivotal study, the primary efficacy endpoint is the change from study baseline (Screening Visit) to Visit Week 52 in the General Conceptual Ability (GCA) score as measured by the DAS-II. The primary analysis will compare the treatment groups using a linear mixed model repeated measures (MMRM) analysis (Malinckrodt et al. 2008; Siddiqui et al. 2009). The repeated measures are the change from baseline GCA score obtained at the scheduled Visit Weeks 16, 28, 40, and 52, respectively. The model will include fixed categorical effects for treatment, visit week, treatment by visit week interaction, baseline GCA classification factor (either ≤ 70 or > 70), baseline age group (either < 6 years or ≥ 6 years), treatment by baseline GCA classification factor interaction, treatment by baseline age group interaction, interaction between baseline GCA classification factor and baseline age group, genotype, and the baseline GCA score as a continuous covariate. Visit week is defined as nominal visits, unless specified otherwise.

SAS Proc Mixed with restricted maximum likelihood estimation (REML) and an unstructured within-patient covariance structure will be used. If this model fails to converge, a first order autoregressive (AR(1)) covariance structure will be used for the primary analysis. Due to small sample size of ITT Population with baseline age ≥ 6 years, MMRM model may fail to converge when low count of subjects with baseline age ≥ 6 years exists in either treatment group. If this model fails to converge, the treatment by baseline age group interaction and /or interaction between baseline GCA classification factor and baseline age group will be removed from the model. The Kenward-Roger approximation will be used to estimate denominator degrees of freedom for tests of fixed effects. The assumptions of the model, including normality, will be evaluated using residual and other diagnostic plots of model fit.

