6.7.5.4 Rate of Change in GCA Score Analysis

The endpoint of rate of change analysis is the slope estimate from the linear regression of GCA score over time for each subject. Only subjects with at least 3 available GCA scores will be included in this analysis.

The slope estimate will be compared between the two treatment groups in HIT-HGT-094 using one-way ANOVA. The response variable in the ANOVA model is the weighted linear regression slope, where the weight is the inverse of one plus the sum of mean squared error (MSE) from the linear regression, i.e. $1/(1+\text{MSE})$.

The sample SAS code is presented in [appendix 9.2.5](#).

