6.9.3 Pharmacokinetic Parameters

The pharmacokinetic analysis will be conducted by the pharmacokinetics CRO for Clinical Pharmacology and Pharmacokinetics Department of Shire Pharmaceuticals using Phoenix WinNonlin version 6.2 or higher (Pharsight Corporation, Mountain View, California, USA).

Pharmacokinetic parameters will be determined from serum concentration-time data using noncompartmental methods and all calculations will be based on actual sampling times. Serum concentration vs. time will be plotted for each patient. Mean serum concentration vs. time curves will also be presented by dose (5 mg, 7.5 mg, and 10 mg) and visit (Week 4, Week 24, and Week 48).

The pharmacokinetic parameters to be determined will include, but not be limited to, the following:

C_{\max}	Maximum concentration occurring at t_{\max}
t_{\max}	Time of maximum observed concentration sampled during a dosing interval
$t_{1/2}$	Terminal half-life
$AUC_{0-\infty}$	Area under the curve extrapolated to infinity, calculated using the observed value of the last non-zero concentration
AUC_{0-t}	Area under the curve from the time of dosing to the last measurable concentration
CL/F	Total body clearance for extravascular administration divided by the fraction of dose absorbed
V_z/F	Volume of distribution associated with the terminal slope following

λ_z extravascular administration divided by the fraction of dose absorbed
First order rate constant associated with the terminal (log-linear) portion of the curve

CL/F and Vz/F will also be corrected for body weight.

Summary statistics (number of observations, mean, standard deviation, coefficient of variation, median, maximum, minimum, and geometric mean) will be determined for all pharmacokinetic parameters and presented by bioanalytical method (ELISA, LC-MS/MS), dose and visit. Serum and CSF concentrations of idursulfase at each nominal sampling time will also be summarized by bioanalytical method, dose and visit using descriptive statistics.

The association of the presence of anti-idursulfase antibodies and idursulfase concentration-time profiles and pharmacokinetic parameters will be evaluated, if applicable.

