8.2 Handling of Dropouts or Missing Data

For randomized patients who discontinue early from the study, their early EOS efficacy evaluations will be used for the next scheduled time point only if the EOS evaluation is performed within 45 days of the next scheduled visit. In general, no further imputation will be used for descriptive analyses, or for primary and secondary efficacy analyses utilizing MMRM methodology.

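### The exploratory GCA slope is fitted on nominal visit week, so Screening and moved early end-of-study scores are misdated, by an amount and sign that turn on an unstated Screening code

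*SAP*

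**What the plan says.** SAP 6.7.5.4 gives the endpoint: "The endpoint of rate of change analysis is the slope estimate from the linear regression of GCA score over time for each subject". It does not say how time is measured. The only place that does is the sample code in SAP 9.2.5, which fits "model GCA = VisitWk" to each boy's data with visit week as a numeric regressor.

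The rest of the SAP makes that variable nominal. SAP 6.7.1 states "Visit week is defined as nominal visits, unless specified otherwise". SAP 8.8 adds that "nominal visits will be used for the per-visit analyses" and allows off-schedule neurodevelopmental tests to be assigned to them.

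Four further provisions decide which scores are misdated:

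- **Baseline.** SAP 6.1: "Baseline is defined as the value at Screening Visit for all parameters, unless specified otherwise". SAP 4.1 places Screening between Day -28 and Day -1. No section gives it a single numeric visit week.
- **Early withdrawal, SAP 8.2.** A patient's "early EOS efficacy evaluations will be used for the next scheduled time point", provided the evaluation falls within 45 days of that visit.
- **Early withdrawal, SAP 8.8.** An early termination visit counts for a scheduled visit only if it falls inside the protocol window, which is ±7 days.
- **Minimum data, SAP 6.7.5.4.** "Only subjects with at least 3 available GCA scores will be included in this analysis".

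For pharmacokinetics, SAP 6.9.3 takes the other course: "all calculations will be based on actual sampling times".

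**The concern.** A slope is points per unit of time, so an error in the time axis is an error in the endpoint. A model with visit as a category tolerates nominal labels; a per-patient regression uses them as numbers.

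No single code can date Screening correctly for every boy, because the true date varies over four weeks. The sponsor treats the pre-treatment interval as material: SAP 4.2 allows up to two months between the Screening assessment and first treatment, and charges 2 points of decline to it. An early end-of-study score placed at a later visit stretches time at the other end and flattens the slope.

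The error in a slope is proportional to the slope itself. It is therefore larger in an arm that declines than in one that is stable, and it need not cancel from the estimated treatment difference.

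**Working it through.** **The plan's own figures.** The documents give no figure for the slope analysis. The nearest is the primary power in SAP 4.2: 80% with 32 and 16 patients, difference 11, SD 11.6, two-sided 5%, 10% missing. With 28.8 and 14.4 evaluable, the noncentrality is 11 / (11.6 × √(1/28.8 + 1/14.4)) = 2.94 and the power is 81.8%, so the figure reproduces.

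**Inputs.** DAS-II tests at Screening and Weeks 16, 28, 40 and 52; control decline of 1 point per 28 days, or 0.25 points per week (SAP 4.2 and 9.3.2). Assumed, because the SAP is silent: the Screening score enters the slope, with code 0 or -4.

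**Formula.** For an exactly linear decline, fitted slope / true slope = Σ(x − x̄)a / Σ(x − x̄)², where x is the nominal and a the actual week.

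**Screening coded 0, five scores.** x̄ = 27.2 and Σ(x − x̄)² = 1644.8. A test s weeks before Day 0 gives an error of 27.2s / 1644.8:

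- s = 1: +1.7%
- s = 2: +3.3%
- s = 4: +6.6%

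**Screening coded -4, five scores.** x̄ = 26.4 and Σ(x − x̄)² = 1875.2. The error is −30.4(4 − s) / 1875.2:

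- s = 1: −4.9%
- s = 2: −3.2%
- s = 4: 0%

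**Early end-of-study score moved 45 days (6.43 weeks), Screening dated correctly.**

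| Moved to | Scores | Calculation | Error |
|---|---|---|---|
| Week 52 | 5 | 24.8 × 6.43 / 1644.8 | −9.7% |
| Week 40 | 4 | 19 × 6.43 / 876 | −13.9% |
| Week 28 | 3 | 13.33 × 6.43 / 394.7 | −21.7% |

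If only a one-week move is allowed, as under SAP 8.8, the errors are −1.5%, −2.2% and −3.4%. The two sources can offset: Screening 4 weeks before Day 0 and coded 0, with a 45-day move to Week 52, gives +6.6% − 9.7% = −3.1%.

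**Ordinary visit windows.** The worst ±7-day pattern for a completer (Weeks 15, 27, 41 and 53) gives 48.0 / 1644.8 = 2.9%, in either direction.

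**Between-arm effect.** 4000 simulated trials, 32 against 16, used the SDs (3, 5, 8, 10) and AR(1) correlation of 0.80 from SAP 9.3.2. Screening was uniform over Days -28 to -1 and coded 0, and visits were uniform within ±7 days. Treated boys were stable from Week 4, all data were complete, and slopes were unweighted.

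| | Nominal weeks | Actual dates |
|---|---|---|
| Control slope, points per 52 weeks | −13.41 | −12.97 |
| Arm difference, points per 52 weeks | 12.12 | 11.69 |
| Power | 96.5% | 96.5% |
| Type I error | 4.7% | 4.7% |

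The difference is 12.12 / 11.69 − 1 = 3.7% too large. A separate, smaller simulation gave 0.2575 against a true 0.25 points per week, or 3.0%. With no treatment effect, the mean difference was about zero on either scale.

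**The case against.** The best case for leaving the code alone is that little depends on it. The slope is exploratory and outside the three families tested under SAP 8.5. The code is labelled as a sample, and the governing text says only that scores are regressed over time. The pharmacokinetic comparison is weak too, since those profiles run over 36 hours. All of this bears on priority. It does not supply a time axis: the caveat in SAP 9.2 covers only dataset and variable names, and no other text names the regressor.

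A reader might go further than the documents allow in five ways:

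- **A fixed error of several percent.** Size and sign depend on a Screening code that is not given. No section even says outright that the Screening score enters; if it does not, that part of the point falls away.
- **Every early-withdrawal score is badly misdated.** The 10% to 22% range needs a full 45-day move. SAP 8.8 would limit the move to the visit window, and a test inside a window is barely misdated.
- **An invalid treatment test.** The unweighted test performs the same on either time scale.
- **A boy with three dated scores is excluded.** A test at about Weeks 17 to 21 lies more than 45 days before Week 28, so SAP 8.2 gives it no visit. That the three-score rule then drops him is an inference; the rule speaks of available scores, and SAP 8.8 lets off-schedule tests be assigned to visits.
- **A change with no downside.** Such a boy, once admitted, has an imprecise slope. With equal noise per score, his standard error is √(1644.8 / 240.7) = 2.6 times (third test at Week 21) to √(1644.8 / 182) = 3.0 times (Week 17) that of a five-visit boy.

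It is also fair to say that the arms are not compared on the slope itself. SAP 9.2.5 compares slope / (1 + MSE), which in the same simulation cut the difference from 12.1 to 2.2 points per 52 weeks and power from 96.5% to 79.6%. That is a larger, separate defect; correcting it would still leave the time axis wrong.

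**Conclusion.** The point stands as a cheap improvement. Run as written, the analysis misdates the Screening score and any early end-of-study score that is moved to a later visit.

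For a completer screened 1 to 4 weeks before Day 0, the slope error is about +2% to +7% if Screening is coded 0 and about −5% to 0% if it is coded -4. A full 45-day move makes the slope about 10% to 22% too shallow with Screening dated correctly, and less under SAP 8.8's limit.

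With Screening coded 0, the unweighted arm difference is about 3% to 4% too large. Power and type I error hardly change, so the damage is to the estimate and not to error control. These figures assume linear decline, inclusion of the Screening score and, for the arm comparison, complete data. Unequal early withdrawal could affect the arms differently and was not simulated.

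**What to change.** In SAP 6.7.5.4 and 9.2.5, replace visit week by (actual DAS-II date − Screening DAS-II date) / 7. Enter each valid GCA score at its own date, without moving early end-of-study scores, and count dated scores for the three-score rule. The choice of origin does not affect the slope.

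Separately, reconcile SAP 8.2 and 8.8 on early evaluations. Actual dates remove the conflict for the slope only; the per-visit analyses still need one rule.

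The cost is one derived variable and a few sentences. Test dates should be at hand, since SAP 6.7.3 already needs chronological age for the developmental quotient. The primary analysis is untouched.

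The downside is the few early withdrawals with short follow-up, whose slopes are imprecise. This matters more while the response is slope / (1 + MSE): with three scores the MSE has one degree of freedom and can be near zero, so a very noisy slope can be left almost unshrunk. That weighting should be dealt with as its own item.

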9.2.6 Sample SAS code for the multiplicity analysis

```
proc multtest inpvalues=rawp hommel;  
run;
```

Dataset rawp contains the raw p-values from hypothesis tests for the change from baseline to Visit Week 52 using MMRM analysis for the following 6 endpoints:

- Verbal, Nonverbal and Spatial standard scores from the DAS-II;
- Communication, Daily Living Skills and Socialization standard scores from the VABS-II;

9.2.7 Sample SAS code for sensitivity analysis using WOCF

- ANCOVA-WOCF

```
proc mixed data=adefwocf;  
  class GCAclass Agegroup Trt;  
  model GCAchgBL = GCAclass Agegroup Trt GCABL AgeBL;  
  estimate "Diff. at month 13" Trt 1 -1/cl;  
  lsmeans Trt /cl;  
  ods output Estimates=E_ANCOVA;  
  where VisitWk=52;  
run;
```

- vE-WOCF;

```
proc npar1way data=adefwocf ;  
  strata Agegroup GCAclass;  
  class Trt;  
  var GCAchgBL;  
  where VisitWk=52;  
run;
```

9.2.8 Sample SAS code for sensitivity analysis using PMMs with control-based pattern imputation

A total of 1000 sets of posterior mean and co-variance estimates are extracted from the SAS MI procedure using the available non-missing placebo data. Five hundred of the posterior sets will be applied to the pooled active treatment group, while the other 500 will be applied to the placebo group. One set of imputations for all missing values will be generated based on each variation of posterior estimates. All 500 datasets for imputations within a treatment group will be ordered from 1 to 500 and combined between pooled active treatment group and placebo, for a total of 500 completely imputed datasets.

```
*Step 1;  
proc mi data=unimputed out=discard nimpute=1000 seed=609 noprint;  
  where Trt=0; *where 0 is placebo;  
  var GCABL GCA_wk16-GCA_wk52;  
  mcmc outest=posterior; *picks up the placebo posteriors;  
run;
```

```
*500 posteriors for the placebo, rest for active;  
data posteriors(type=est);  
  set posteriors;  
  if 1<=_imputation_<=500 then do; *assign placebo posteriors;  
    Trt=0;  
  end;  
  if 500<_imputation_<=1000 then do; *assign posteriors to active;  
    Trt=1;  
    _imputation_=_imputation_-500;  
  end;  
run;
```

```
proc sort data=unimputed;  
  by Trt;  
run;
```

```
proc mi data=unimputed out=imputed;  
  by Trt;  
  var GCABL GCA_wk16-GCA_wk52;  
  mcmc inest=posterior; *use the placebo posteriors;  
run;
```

```
*Step 2;  
data endpoint;  
  set imputed;  
  endpoint= GCA_wk52-GCABL;  
run;
```

```
proc sort data=endpoint;  
  by _imputation_;  
run;
```

```
proc mixed data= endpoint;  
  class GCAclass Agegroup Trt;  
  model endpoint = GCAclass Agegroup Trt GCABL AgeBL;  
  by imputation ;  
  estimate "Diff. at month 13" Trt 1 -1/cl;  
  lsmeans Trt /cl;
```

```
ods output Estimates=E_ANCOVA;  
run;
```

```
*Step 3;  
proc sort data= E_ANCOVA;  
  by label _imputation_ ;  
run;
```

```
proc mianalyze data= E_ANCOVA;  
  by label;  
  modeleffects estimate;  
  stderr stderr;  
run;
```

Repeat the process above for the key 2nd endpoint.

9.2.9 Sample SAS code for the subgroup analysis with baseline age < 6 years, baseline age < 55 months and baseline age ≥ 55 months

```
ods output estimates=est Tests3=FixF;  
ods graphics on;  
proc mixed data=adef_subgroup covtest;  
  class Trt VisitWk GCAclass Agegroup Genotype usubjid;  
  model GCAchgBL = GCAclass Trt VisitWk Trt*Visitwk Trt* GCAclass GCABL  
  Genotype/ ddfm=KR residual;  
  repeated VisitWk / type=un subject=usubjid rcorr;  
  estimate "Trt diff at Week 16" Trt 1 -1 Trt*VisitWk 1 0 0 0 -1 0 0 0 / cl;  
  estimate "Trt diff at Week 28" Trt 1 -1 Trt*VisitWk 0 1 0 0 0 -1 0 0 / cl;  
  estimate "Trt diff at Week 40" Trt 1 -1 Trt*VisitWk 0 0 1 0 0 0 -1 0 / cl;  
  estimate "Trt diff at Week 52" Trt 1 -1 Trt*VisitWk 0 0 0 1 0 0 0 -1 / cl;  
  lsmeans Trt*VisitWk / cl;  
run;
```

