From this model, least squares means, standard errors, treatment differences in least squares means, and 95% confidence intervals will be estimated for each time point. Primary inference will be based on the treatment comparison of least squares means at Visit Week 52 from this model, and a p-value will be presented for this time point only. The null hypothesis is that the mean difference in the primary endpoint between the two treatment groups is zero, versus the alternative hypothesis that this difference is not zero. The hypotheses can be expressed as follows:

$$H_0: \mu_{IT} - \mu_{control} = 0 \text{ versus } H_1: \mu_{IT} - \mu_{control} \neq 0$$

Where μ_{IT} refers to the mean change from baseline to Visit Week 52 in GCA score in the idursulfase-IT treated group and $\mu_{control}$ refers to the mean change from baseline to Visit Week 52 in GCA score in the No IT treatment group. The test will be performed using the final, MMRM model-based t-test with a two-sided significance level of 5%. Estimated least squares means for change from baseline and the observed absolute values (\pm SE) by treatment group will be plotted over time.

The sample SAS code is presented in [appendix 9.2.1](#).

As a sensitivity analysis for the primary analysis using ITT population, MMRM model in the same manner as described above will be conducted for a subset of ITT population, which includes all ITT subjects excluding subjects enrolled from the observational study HGT-HIT-090 who experienced a decrease in GCA score of ≥ 10 points over 12 months in study HGT-HIT-090 prior to being enrolled in study HGT-HIT-094 and a GCA score at HGT-HIT-094 Screening >85 points.

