If the primary or key secondary endpoint is missing in $> 15\%$ of patients in either treatment group, then an MNAR pattern mixture model (PMM) will be fit with control-based multiple imputation, according to the sequential imputation method described by Ratitch and O'Kelly (2011). Five hundred complete datasets will be imputed and the analysis of each imputed dataset will compare the treatment groups at the Visit Week 52 time point using an analysis of covariance (ANCOVA) model. The ANCOVA model will include fixed categorical effects for treatment, baseline GCA classification factor (either ≤ 70 vs. > 70), baseline age group (either < 6 years or ≥ 6 years), and the corresponding baseline score as a continuous covariate. The least squares mean difference estimates will be averaged and the associated SEs will be summarized based on within-imputation and between-imputation variance using the SAS MIANALYZE procedure to yield a final estimate with associated 95% CI and p-value. The sample SAS code is presented in [appendix 9.2.8](#).

If the MMRM model for the primary or key secondary endpoint fails to converge using an unstructured covariance matrix, an AR(1) covariance structure will be used. In this case, additional covariance structures will be tried as sensitivity analyses to assess the robustness of the results, including compound symmetric and Toeplitz structures.

If there are cases in which subjects receive a study treatment that differs from the treatment to which they were randomly assigned, MMRM, ANCOVA-WOCF and WRS-WOCF analyses of the primary and key secondary endpoints will be performed by treatment actually received.

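### In SAP 9.2.8 the treatment contrast runs control minus IT under the coding stated there, and the listing does not deliver the 500 split imputations that the text describes

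*SAP*

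**What the plan says.** SAP 6.7.1 gives the direction of the effect through its null hypothesis, "H_0: \mu_{IT} - \mu_{control} = 0", so a positive difference favours IT. Appendix III of the SAP (9.3.2) also works with active minus control. The primary comparison is a "MMRM model-based t-test with a two-sided significance level of 5" per cent.

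SAP 8.7 adds a control-based pattern mixture analysis if the primary or key secondary endpoint is missing in more than 15% of patients in either arm. It says: "Five hundred complete datasets will be imputed". The introduction to 9.2.8 explains how: 1,000 posterior sets are drawn from the control data, 500 are used for each arm, and these combine into 500 completed datasets.

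The 9.2.8 listing is the only place in the SAP that states a numeric treatment code. Control is identified by "where Trt=0; *where 0 is placebo" and active by the branch "if 500<_imputation_<=1000 then do; *assign posteriors to active", which sets Trt to 1. The final ANCOVA there requests "estimate 'Diff. at month 13' Trt 1 -1/cl". The imputation step reads its posterior draws through "mcmc inest=posterior; *use the placebo posteriors".

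The primary model in 9.2.1 uses the same coefficients, "estimate 'Trt diff at Week 52' Trt 1 -1 Trt*VisitWk 0 0 0 1 0 0 0 -1 / cl", with no coding stated. The opening note of 9.2 says that dataset and variable names may differ in practice.

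**The concern.** There are two separate faults in one listing.

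First, the contrast and the hypothesis point in opposite directions under the coding that 9.2.8 itself gives. Both arms are expected to decline, so the arm means are negative whichever way the difference is taken. A negative treatment difference would therefore not look odd, and a benefit could be read as harm.

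Second, the code does not do what its own introduction says. This is the plan's only control-based sensitivity analysis for data missing not at random. If the listing is followed, it either fails on a dataset that does not exist or, once patched locally, imputes from draws that were never divided between the arms. The number of imputations and the seed would then be left to the programmer.

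**Working it through.** **Sign of the contrast in 9.2.8**

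Inputs: control coded 0 and active coded 1 (9.2.8); coefficients 1 and -1 on Trt, with no ordering option printed (9.2.8); planned mean changes of -13 for control and -2 for IT (SAP 4.2).

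- Plan's own figure, IT minus control: -2 - (-13) = +11. This reproduces the 11 points in SAP 4.2.
- Contrast as coded, with levels in the order 0, 1: (1)(-13) + (-1)(-2) = -11.

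As an illustration, one trial of 16 control and 32 IT patients was simulated with the planned means and an SD of 11.6. It was analysed by ANCOVA on baseline score and GCA stratum:

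| Contrast | Estimate | 95% CI | Two-sided p |
|---|---|---|---|
| Trt 1 -1 (level 0 minus level 1) | -10.66 | -19.06 to -2.27 | 0.0139 |
| Trt -1 1 (IT minus control) | +10.66 | 2.27 to 19.06 | 0.0139 |

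Only the sign of the estimate and of the limits changes.

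**Same coefficients elsewhere**

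Sections 9.2.1, 9.2.2, 9.2.7, 9.2.9 and 9.2.10 use 1 and -1 for Trt but give no coding. If control sorts first, they return control minus IT. If IT sorts first, they already agree with 6.7.1. The lines in 9.2.11 also carry a baseline GCA coefficient, so they are not a plain arm difference and are left out here.

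**Number of imputations in 9.2.8**

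Plan's own figure: 1,000 / 2 = 500 posterior sets per arm. The renumbering rule in the split step is sound. Applied to draws 1 to 1,000, it gives 500 sets for Trt=0 and 500 for Trt=1, each numbered 1 to 500. The trouble lies in what each step reads and writes:

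| Step | Reads | Writes | Comment |
|---|---|---|---|
| First PROC MI (nimpute=1000, seed=609) | `unimputed`, control only | `posterior` | 1,000 draws, no Trt variable |
| Split step | `posteriors` | `posteriors` | input not created by any earlier step |
| Second PROC MI, by Trt | `unimputed`, with draws from `posterior` | `imputed` | unsplit draws; no nimpute, no seed |

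The Trt labels are assigned only in the split step, and that step's output is never used. The listing was traced line by line and the split rule emulated; SAS itself was not run.

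**How likely the analysis is to be needed**

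More than 15% missing means at least 3 of 16 controls (18.75%) or at least 5 of 32 IT patients (15.6%). SAP 4.2 allows for up to 10% missing at Week 52. Assume binomial missingness at that rate, independent between arms:

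- P(at most 2 of 16) = 0.789
- P(at most 4 of 32) = 0.789
- P(triggered) = 1 - 0.789 × 0.789 = 0.38

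The same calculation gives about 6% at a 5% missing rate and 93% at a 20% rate.

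**The case against.** The strongest reply is that this is sample code. Section 9.2 warns that names may change, and the prose specification is clear and correct: IT minus control, 500 datasets, 1,000 draws split evenly. The naming fault would stop the run and be noticed. Arm-level least squares means are requested beside the contrast, so a reversed sign could be spotted. All of this is fair, and it keeps the point minor. But the warning about names covers renaming. It does not cover two names used inconsistently within one listing, a contrast in the wrong direction, or an unstated number of imputations.

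Three stronger readings are tempting, and the documents do not support them.

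- **That the primary and other efficacy tables and forest plots will show reversed signs.** The 0/1 coding appears only in 9.2.8. That section speaks of placebo and a pooled active group, neither of which exists in this trial, so it may be adapted from a template and is weak evidence for how Trt is coded in 9.2.1. If Trt carried text labels such as IT and No IT, IT would sort first and the contrast would be right.
- **That far fewer than 500 imputations would be run.** This depends on how the software sets the count when posterior draws are supplied, which the documents do not say. If a software default applied, the count would be small (assumed 5 or 25, depending on release). If the unsplit draws governed, it could be as high as 1,000. All that can be said is that the number is unspecified.
- **That the ANCOVA is run by a wrong variable.** The line reads `by imputation`, while the neighbouring sort steps have the underscores. They may have been lost when the PDF was read, so this is not counted.

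**Conclusion.** The point holds for 9.2.8. Under the coding stated there, and assuming class levels are taken in ascending order of that code, the contrast is the reverse of the one in 6.7.1: -11 instead of +11 on the planned means, with both confidence limits changing sign. For 9.2.1, 9.2.2, 9.2.7, 9.2.9 and 9.2.10 the finding is conditional: the SAP leaves the direction undefined, which is an omission and not a demonstrated error. Separately, and whatever the coding, the 9.2.8 listing does not carry the 500/500 split into the imputation and does not specify how many imputations are made or from what seed.

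The consequence is limited. Two-sided p-values, power and the gatekeeping sequence are unaffected, and the pattern mixture analysis is a conditional sensitivity analysis. This is a minor correction, but one worth making before database lock, because the trigger is not remote at the missing-data rate the plan allows for.

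**What to change.** 1. State once, at the start of SAP 9.2, how Trt is coded and in what order its levels enter the CLASS statement. Make every ESTIMATE line return IT minus control under that order, and say that positive values favour IT. Do not simply flip the coefficients throughout: if IT sorts first in some listings, that would create the error it is meant to remove.
2. In the split step of 9.2.8, read `posterior` (`set posterior;`) and write `posteriors`.
3. In the second PROC MI of 9.2.8, use `inest=posteriors`, and add `nimpute=500` and a stated seed.
4. While editing, confirm that the BY variable of the ANCOVA in the source file is `_imputation_`.

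The cost is a handful of line edits in the SAP appendix. Nothing in the design, data collection, sample size or planned inference changes.
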